
#### (4) **Work Proposed**

- (a) Provide a timetable describing the sequence of the proposed research.

Staff training, IRB approval and finalization of website specifications and beta testing will occur during the first 6 months of Year 1.

Recruitment and randomization would begin the second half of Year 1: Recruitment will be conducted over 30 months to achieve the goal to randomize up to 185 subjects. We anticipate enrolling 3-4 subjects per site each month through the third quarter of study year 3 (Figures 2 and 3). Between both sites, we expect to screen and enroll a total of 320 participants in order to randomize a total of 185 participants for the whole study.

Subjects will have completed their participation in the study after approximately 13 months from the first in-clinic baseline visit.

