**Figure 2. Gantt Chart**

[figure not shown]
	Yr 1				Yr 2				Yr 3				Yr 4			
Activity	Q1	Q2	Q3	Q4	Q1	Q2	Q3	Q4	Q1	Q2	Q3	Q4	Q1	Q2	Q3	Q4
Train Staff																
Obtain IRB Approval																
Finalize Website Specifications and Beta Testing of Website																
Enroll and Randomize to WEB Intervention or Control																
Intensive Intervention and Outcomes Data Collection (6 months)																
Maintenance Intervention (6 months)																
Data Cleaning, Analyses, Manuscript Preparation																

(b) It is useful to specifically relate each experiment to particular hypotheses and/or key questions. Describe the research design, methods, and procedures to be used to accomplish the specific aims of the application.

At VA Boston and VA Birmingham, a total of 185 subjects with COPD will be randomized with an allocation ratio of 1:1 to one of 2 arms: (1) written instructions and education to exercise (usual care) or (2) pedometer and Internet-mediated walking program. Subjects will participate

in the study for a total of up to 13 months, depending on the timing of the C12 in-clinic study visit. The intensive interventional phase will be 6 months followed by a maintenance intervention phase of 6 months and a subsequent 14-day step count collection using a pedometer at 12-months (up to 13 months). Six-minute walk test distance at 6 months will be the primary outcome to assess the efficacy of the Internet-mediated, pedometer-based walking program. Since we are studying the efficacy of a walking intervention, the 6MWT distance is the primary outcome of choice. Secondary outcomes include HRQL, dyspnea, CRP and IL-6 levels, risk of AEs and COPD-related hospitalizations, engagement in PA assessed by daily step count. Additional secondary outcomes include body composition (adiposity) and bone mineral density at baseline and 12 months (in the subset of subjects enrolled at VA Boston only). The study contact timeline and assessments are summarized in Figure 3. Subjects will have an in-clinic assessment at baseline, 3, 6, and 12 months, and a telephone call at 9 months. We anticipate drop-out at 6 months to be at most 40%, resulting in at least 55 subjects who will complete each arm of the study.

**Figure 3.** Protocol Summary. C=Clinic visit, P=Phone call.

**Inclusion Criteria** are:

- a) Male and female subjects, greater than or equal to 40 years of age

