**Power Calculation:** This study is powered on our pre-specified primary outcome of 6MWT distance. Our main comparison is 6MWT distance at 6 months between the WEB intervention and control arms. Our power analysis is based on a widely accepted minimum clinically meaningful change in 6MWT distance of 54 meters and the published standard deviation for 6MWT distance of 80-120 meters (90). Our data in a similar Veteran population showed a standard deviation of 102 meters for 6MWT distance. We use a standard deviation of 100 meters in our power calculation. Using the sample size formula for the comparison of the means of 2 independent samples, we calculate that 55 evaluable subjects in each arm at 6 months will allow

[figure not shown]

detection of a difference of at least 54 meters between the WEB and usual care arms with a power of 80% and  $\alpha=0.05$ . We anticipate a maximal drop-out of 40% at 6 months. In order to have 111 evaluable subjects at 6 months, we plan to enroll a total of 185 subjects.

**Secondary Aims:** To estimate the effect of the WEB intervention on (a) HRQL, as measured by the St. George's Respiratory Questionnaire (SGRQ), (b) dyspnea, (c) CRP and IL-6, (d) risk of AEs and COPD-related hospitalizations, (e) engagement in PA as measured by daily step count, (f) body composition and bone mineral density, and (g) pain.

Our statistical analysis plan for the secondary outcomes is similar to that for the primary outcome. We will use 2-way factor analysis or analysis of variance (ANOVA) to assess the effect of intervention versus control on SGRQ-TS, dyspnea score, CRP and IL-6, and daily step count. We will analyze absolute values of the secondary outcomes at baseline and 6 months. Two-way ANOVA will allow us to examine the effect of our intervention, and additionally allow us to assess the interaction between treatment and time (treatment-time) on the secondary outcomes. We will use a mixed model (PROC MIXED in SAS) to perform the 2-way ANOVA. Models will have SGRQ-TS, dyspnea score, CRP and IL-6, or daily step count as the dependent variable, and treatment, time, and treatment-time as independent variables. Models will also include study site and any unbalanced baseline characteristics as covariates.

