**Power Calculations:** A sample size of 111 evaluable subjects at 6 months determined by the primary outcome of 6MWT distance will also allow detection of significant differences in the secondary outcomes. Using the sample size formula for the comparison of the means of 2 independent samples, we can detect an effect size of 0.55 SD units with 80% power and  $\alpha=0.05$ . Using the SD's obtained from our cross-sectional observational study, we can detect a change of at least 10 units in SGRQ-TS, 1.8 mg/L in CRP level, and 0.59 pg/mL in IL-6 level. In addition, as an estimate for anticipated differences between arms, we examined the mean 6MWT distance, SGRQ-TS, CRP, and IL-6 levels in those who walked above and in those who walked below the median daily step count in our observational data. We observed a difference of 1.27 pg/mL in IL-6 in those who walked above and in those who walked below the median daily step count, values greater than our detectable difference suggesting sufficient power. We found a difference of 7 units in SGRQ-TS and 0.96 mg/L in CRP. While these preliminary observed estimates of difference in SGRQ-TS and CRP are slightly smaller than our calculated detectable estimates, we anticipate there will be sufficient power to detect differences in these secondary outcomes when the analyzed groups are differentiated by the WEB intervention, since our power calculations based on groups dichotomized at the median step count are conservative. In calculating power for detecting differences in risk of AEs, we expect to observe 106 AEs in the 111 subjects completing a 12-month follow-up period based on our preliminary data. Given this rate and using the POISS\_SS macro of E. Bergstralh (a Poisson power calculator), we will be able to detect a rate ratio of at least 1.70 with 80% power and 1.85 with 90% power. Again, to estimate anticipated observed differences between treatment arms, we examined the number of AEs in those who walked above and in those who walked below the median daily step count in our observational data. One hundred thirty-six AEs were observed in those who walked below the median daily step count and 76 AEs were observed in those who walked above the median daily step count, an observed rate ratio of 1.79, indicating adequate power.

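### The 0.55 SD at 80% power stated for the secondary outcomes does not apply to body composition and bone density, which are measured at VA Boston only and at month 12

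*Combined protocol and SAP*

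**What the plan says.** In the statistics section, the power paragraph for the secondary aims starts from "A sample size of 111 evaluable subjects at 6 months determined by the primary outcome of 6MWT distance" and says that this number "will also allow detection of significant differences in the secondary outcomes". It then states "we can detect an effect size of 0.55 SD units with 80% power" at alpha 0.05. No outcome is excepted.

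The list of secondary aims just before it ends with "f) body composition and bone mineral density, and (g) pain". Work Proposed, part (b), describes these measurements as additional secondary outcomes: "body composition (adiposity) and bone mineral density at baseline and 12 months (in the subset of subjects enrolled at VA Boston only". Table 5 and item f of the outcome assessments (D.6) repeat the site restriction and the two time points.

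The Anticipated Results paragraph for the secondary aims expects lower adiposity and higher BMD in the intervention arm at 6 months. Table 5 has no DXA scan at month 6.

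The documents give no size for the DXA subset, no detectable effect for it and no site quota. On recruitment, the timetable says "We anticipate enrolling 3-4 subjects per site each month", for two sites.

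**The concern.** A reader who wants to know what the trial can show on body composition or BMD finds one figure, 0.55 SD at 80% power, attached to the secondary outcomes as a group. That figure needs both sites and all 111 subjects. The DXA comparison has one site, and its follow-up scan comes six months after the time point on which the 111 is based.

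What is at stake is interpretation. The plan predicts a direction for both DXA outcomes. If the comparison is null and is read against 80% power at 0.55 SD, it will look like firmer evidence against a moderate effect than the design can supply.

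**Working it through.** **Inputs from the documents**
- 111 evaluable subjects from 185 randomized, 1:1 allocation: "a total of 185 subjects with COPD will be randomized with an allocation ratio of 1:1".
- Method: "Using the sample size formula for the comparison of the means of 2 independent samples". Alpha is 0.05. Sidedness is not stated; two-sided is assumed because it fits the plan's figure (one-sided would give 89% power at 0.55 SD).
- Retention of at least 60% at 6 months (185 × 0.60 = 111). No separate 12-month retention figure is given, but the exacerbation power calculation counts the same 111 as completing 12 months.

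**Assumption not in the documents**
- Boston share of 50%, inferred from the same planned monthly rate at each of two sites. It is varied below.

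**Formulas.** With n per arm and an effect of d SD units, power ≈ Φ(d·√(n/2) − 1.96), and the effect detectable at 80% power ≈ 2.80·√(2/n). The figures below use the noncentral t version, which runs one to two points lower in power.

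**Step 1: reproduce the plan's figure.** For 111 subjects, n = 55.5 per arm. Normal approximation: 0.55 × √27.75 − 1.96 = 0.94, so power is 83%. The t version gives 81.9%, with a detectable effect of 0.537 SD. The stated 0.55 SD at 80% is correct, and slightly conservative, for the full sample.

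**Step 2: a 50% Boston share, by month-12 retention.** About 185 × 0.5 = 92 randomized at Boston.

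| Retention | Scans | Power at 0.55 SD | Detectable at 80% power |
|---|---|---|---|
| 60% | about 55 | 52% | 0.77 SD |
| 90% | about 83 | 70% | 0.62 SD |
| 96% | about 88 | 72% | 0.60 SD |
| 100% | about 92 | 74% | 0.59 SD |

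If a further 10% or 20% of the 55 were lost between months 6 and 12 (assumed), about 50 or 44 scans would remain, with power of 48% or 43%.

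**Step 3: other shares at 60% retention.** A 40% share (0.4 × 111 ≈ 44 scans) gives 43% power and 0.86 SD. A two-thirds share (74 scans) gives 65% and 0.66 SD.

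**Step 4: what 80% would need.** At 0.55 SD the t version needs 53 per arm, or 106 scans. That is 106/111 = 95% of all evaluable subjects at 60% retention, or 106/185 = 57% of all randomized subjects if nobody were lost. A 50% share therefore falls short at any retention. A two-thirds share (about 123 randomized) would reach 80% only with retention of about 106/123 = 86% or better.

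**The case against.** The strongest reply is that the paragraph was never meant to cover DXA. It speaks of 6 months; its worked examples are the SGRQ total score, CRP, IL-6 and exacerbations; and the outcomes named for the 6-month mixed model leave out body composition and BMD. The aims section also words the secondary aims as estimation and says that (f) is measured in a subset, so the restriction is disclosed. This stands to the extent that no sentence claims 80% power for DXA by name, and the documents do not support a reading that the subset was concealed. It does not remove the problem: the opening sentence is unqualified, aim (f) is in the list it refers to, and no other DXA figure exists.

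A reader might infer that 52% is the power of the DXA comparison. The documents do not support that. The Boston share is inferred. Sixty percent is the plan's floor for retention, and the attrition section reports 0% to 4% loss at 12 months in the team's other COPD studies. Nor is 0.55 SD an effect hypothesised for DXA; it follows from a sample sized on 6MWT distance. Using the baseline scan could also raise power: with about 55 scans, assumed baseline to month-12 correlations of 0.5 or 0.7 would give about 66% or 82% (normal approximation). But the documents give no correlation, the plan's figure rests on two independent means, and body composition and BMD are not among the outcomes named for modelling. The stated 0.55 SD cannot be defended on that ground.

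A reader might also infer an arithmetic error, or an underpowered trial. Step 1 rules out the first for the full sample, and the primary comparison does not depend on this paragraph.

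**Conclusion.** Wrong as written, in the scope of a stated power figure and not in its arithmetic. The sample size, the time point and therefore the 0.55 SD do not apply to body composition or BMD.

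On the plan's unadjusted method and an assumed 50% Boston share, power at 0.55 SD is between about 52% (60% retention) and 74% (no loss), with detectable effects of about 0.77 down to 0.59 SD. At 60% retention, shares from 40% to two-thirds give 43% to 65%. That 80% is missed is firm at a 50% share; it would not hold if Boston supplied well over half of the subjects and retention were high. The number of scans may also be lower than shown, because subjects may decline assessments and pregnant or nursing women are not scanned.

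The 6-month expectation for adiposity and BMD contradicts the assessment schedule whatever the site share. The primary aim and the overall sample size are unaffected.

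**What to change.** 1. In the secondary power paragraph, limit the 0.55 SD statement to continuous outcomes measured in all participants at month 6.
2. Add a line for DXA with the expected number of Boston subjects scanned at month 12 and its range, and the detectable effect on the same method (about 0.6 to 0.8 SD at a 50% share, unadjusted). State that these outcomes will be reported as estimates with confidence intervals, which agrees with the estimation and subset wording of the aims. The sponsor should replace the assumed 50% with the planned or actual Boston share.
3. In Anticipated Results, separate adiposity and BMD from the 6-month outcomes and tie them to month 12, the only follow-up scan in Table 5.

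The cost is a few sentences of text, with no added patients, visits or procedures.

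### Power is called sufficient for SGRQ total score and CRP, but the plan's own formula gives about 52% and 33% at its anticipated differences

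*Combined protocol and SAP*

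**What the plan says.** All of this is in the Statistics (power analysis) section, mainly in the Power Calculations paragraph for the secondary aims. That paragraph opens by saying that the 111 evaluable subjects set by the primary outcome will also be enough to find significant differences in the secondary outcomes. It uses the formula for two independent means, with a detectable effect of 0.55 SD at 80% power and alpha 0.05, and converts this to outcome units: "we can detect a change of at least 10 units in SGRQ-TS, 1.8 mg/L in CRP level, and 0.59 pg/mL in IL-6 level".

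It then takes the anticipated between-arm differences from earlier observational data, comparing people above and below the median daily step count. For IL-6 the observed 1.27 pg/mL is set against the detectable 0.59 and described as "values greater than our detectable difference suggesting sufficient power". For the other two: "We found a difference of 7 units in SGRQ-TS and 0.96 mg/L in CRP". The plan says these "are slightly smaller than our calculated detectable estimates", but concludes "we anticipate there will be sufficient power to detect differences in these secondary outcomes when the analyzed groups are differentiated by the WEB intervention", the reason being "since our power calculations based on groups dichotomized at the median step count are conservative".

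Two related statements in the same section matter here. On retention: "We anticipate a maximal drop-out of 40% at 6 months". On the analysis: "We will analyze absolute values of the secondary outcomes at baseline and 6 months", in a mixed model with treatment, time and their interaction.

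**The concern.** The plan applies a simple test to IL-6: power is sufficient if the anticipated difference exceeds the difference detectable with 80% power. SGRQ total score and CRP fail that test and are still declared sufficiently powered. The shortfall is described as slight when it is 30% for SGRQ and 47% for CRP. What fills the gap is the assertion that a median split understates what the intervention will achieve, and no effect size or ratio is offered for it.

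Health-related quality of life and the inflammatory markers are named secondary aims (a) and (c). If sufficient power is on record, a non-significant CRP result could be read as evidence of no effect when the trial had about a one-in-three chance, by this formula, of detecting the difference the plan itself anticipates.

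**Working it through.** **Inputs, all from Statistics (power analysis)**

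- 55 evaluable per arm at 6 months (111 in total). This follows from 185 randomized 1:1 and 40% drop-out: 185 × 0.60 = 111.
- Detectable effect 0.55 SD, 80% power, alpha 0.05. The number of sides is not stated. Two-sided is assumed, because one-sided testing would give about 89% at 0.55 SD.
- Detectable differences: 10 units (SGRQ), 1.8 mg/L (CRP), 0.59 pg/mL (IL-6).
- Anticipated differences: 7 units, 0.96 mg/L, 1.27 pg/mL.

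**Step 1: reproduce the plan's figure.** Two-sample t power uses a noncentral t with df = 2n − 2 and noncentrality d√(n/2). With d = 0.55 and n = 55, power is 81.6%. The stated 80% is reproduced.

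**Step 2: recover the SDs.** The document does not print them, so they are the detectable difference divided by 0.55.

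- SGRQ: 10 / 0.55 = 18.2 units
- CRP: 1.8 / 0.55 = 3.27 mg/L

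**Step 3: anticipated effect in SD units.**

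- SGRQ: 7 / 18.18 = 0.385
- CRP: 0.96 / 3.273 = 0.293

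**Step 4: the plan's IL-6 test applied to all three.**

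| Outcome | Anticipated / detectable | Passes? |
|---|---|---|
| IL-6 | 1.27 / 0.59 = 2.15 | yes |
| SGRQ | 7 / 10 = 0.70 | no |
| CRP | 0.96 / 1.8 = 0.53 | no |

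**Step 5: unadjusted power at the anticipated differences.**

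| Evaluable per arm | SGRQ, 7 units | CRP, 0.96 mg/L |
|---|---|---|
| 55 (40% drop-out) | 52% | 33% |
| 88.8 (4% loss: 185 × 0.96 / 2) | 72% | 49% |
| 92.5 (no loss: 185 / 2) | 74% | 51% |

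Reaching 80% needs 107 evaluable per arm for SGRQ and 184 for CRP. Equivalently, at the planned size the randomized difference would have to be 10 / 7 = 1.4 times (SGRQ) and 1.8 / 0.96 = 1.9 times (CRP) the median-split difference.

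**Step 6: rounding of the printed figures.** At 55 per arm, letting 7 stand for 6.5–7.5 and 10 for 9.5–10.5 gives 42–62% for SGRQ. Letting 0.96 stand for 0.955–0.965 and 1.8 for 1.75–1.85 gives 31–35% for CRP. Neither approaches 80%.

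**Step 7: precision.** The unadjusted 95% half-width is t(0.975, 108) × SD × √(2/55), with t = 1.982.

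- SGRQ: 6.9 units (6.5–7.2 over the rounding of the 10)
- CRP: 1.2 mg/L

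An observed 7-unit difference would sit at the edge of excluding zero. An observed 0.96 mg/L would not exclude it.

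**Step 8: what a baseline value could add.** The document gives no baseline-to-6-month correlation r, so r is an assumption here. Baseline adjustment divides the SD-scale effect by √(1 − r²). A change contrast divides it by √(2(1 − r)). At 55 per arm:

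| Assumed r | SGRQ adjusted | CRP adjusted | SGRQ change | CRP change |
|---|---|---|---|---|
| 0.5 | 64% | 42% | 52% | 33% |
| 0.7 | 80% | 57% | 73% | 50% |
| 0.8 | 92% | 72% | 89% | 67% |

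**The case against.** The strongest reply is that no printed number is wrong. The 0.55 SD figure reproduces, the detectable and anticipated differences are both shown, and the plan says openly that two of them fall short and words its conclusion as an expectation. That is right: the fault is a conclusion the figures do not support and a gap that is understated. The opening sentence of the paragraph, however, carries no such hedge.

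A second reply is that 52% and 33% describe the worst retention and a test the trial will not run. The 40% is a maximum, and Minimizing Attrition and Handling Missing Data reports 0–4% loss at 12 months in the investigators' other COPD studies. The planned model also uses baseline values. If 4% loss and a high correlation are assumed together (88.8 per arm), baseline-adjusted power at r = 0.5, 0.7 and 0.8 is about 84%, 95% and 99% for SGRQ and 61%, 78% and 90% for CRP. So low power under the planned model is not proven, least of all for SGRQ. This stands as a limit on what can be concluded. It does not rescue the claim: the paragraph argues from the unadjusted formula, and the document gives no correlation to argue from otherwise. Better retention alone leaves both outcomes below 80%.

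A third reply is that earlier trials of the program support a larger effect. The Rationale of the Brain MRI Scan Substudy addendum does say that quality of life improved in two randomized studies, but it gives no effect size, and it says nothing about CRP.

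Finally, these are secondary outcomes, the aims are worded as estimation, and nothing says confidence intervals will be left out. That limits the consequence, and it also makes the correction easy.

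**Conclusion.** The concern holds. By the plan's own unadjusted formula, at 55 evaluable per arm and two-sided 0.05, power at the anticipated differences is about 52% for SGRQ total score (42–62% allowing for rounding) and 33% for CRP (31–35%). Even complete retention gives about 74% and 51%. The statement of sufficient power is therefore not supported by the calculation it follows, and the claim that the median split is conservative is not quantified anywhere in the document.

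The result rests on SDs recovered from rounded figures and on a two-sided test. It does not establish the power of the mixed model. At 55 per arm and an assumed correlation of 0.5–0.8, SGRQ could reach 80% and CRP would not. The IL-6 statement, the primary outcome and the sample size are not affected.

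**What to change.** 1. In the secondary-outcome Power Calculations paragraph, replace the sufficiency claim with wording such as:

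   > Unadjusted two-sample comparison, two-sided 0.05: at 40% drop-out (55 per arm), power is about 52% for 7 SGRQ total-score units and 33% for 0.96 mg/L CRP (about 72% and 49% at 4% loss). At 55 per arm, 80% power holds only for differences of about 10 units and 1.8 mg/L.

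   Delete the descriptions of the gap as slight and of the median split as conservative. For the continuous outcomes, restrict the paragraph's opening sentence to differences of about 0.55 SD or more.

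2. State that SGRQ total score and CRP will be reported as between-arm estimates with 95% confidence intervals, in line with the estimation wording of the secondary aims.

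3. As a separate and optional analysis change, compare the arms at 6 months adjusted for each outcome's own baseline value. Do not attach the 52% and 33% to that analysis. If power is quoted for it, show it over an assumed correlation: for r = 0.5–0.8 at 55 per arm, about 64–92% for SGRQ and 42–72% for CRP.

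Items 1 and 2 are wording only. Their price is that the stated power looks less favorable. Item 3 is a small model change using data already collected. None adds patients, visits or measurements.

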Total number of AEs and COPD-related hospitalizations will be summed over the 12-month study period. Independence of individual AEs will be assured by considering subjects to have experienced a new AE only if they had been off of oral steroids and antibiotics for at least 14 days following the previous AE (86). Given the count data and expected Poisson distribution of number of AEs and hospitalizations, negative binomial regression models (PROC GENMOD) will be used to calculate risk ratios for AE and COPD-related hospitalizations (86). The

multivariate regression model will include number of AEs (or hospitalizations) as the dependent variable, treatment group as the main predictor, as well as study site, number of AEs (or hospitalizations) in the year prior to enrollment, and any unbalanced baseline characteristics.

**Body Composition by DXA Scan:** Body composition and regional fat analysis will be performed at the baseline study visit and the 12-month study visit using standard software available from the manufacturer. For regional fat measurements, the left and right arm cuts pass through the shoulder joints and as close to the body as possible. The leg cuts separate the hands and forearms from the legs, starting with a diagonal cut through the femoral necks. The midline separates the right and left legs. The images obtained from one of our subjects demonstrate the standard cuts that define the arms, legs, and trunk (see figure to the left). These data can be also be used to calculate a waist-hip ratio (i.e., ratio of

central fat to hip fat) in a standardized fashion using the same landmarks as illustrated by the regions defined on the soft-tissue image. The DXA software can be used to define standard waist and hip regions that will allow comparability of these measurements throughout the study. The lower boundary of the central or waist region, which is also referred to as the android region (A, see figure), is the cut through the pelvis at the level of the iliac crests. The upper boundary of the android region extends upwards to 20% of the distance between the pelvis and the top of the shoulders and the lateral boundaries are the arm cuts. The upper boundary of the gynoid region of interest (G, see figure) is the region below the pelvis cut that extends downward from 1.5 times the height of the android region. Lateral boundaries of the gynoid region are the outer leg cuts.

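### The stated exacerbation power is Poisson power for 111 twelve-month completers; the planned analysis is negative binomial, with no allowance for overdispersion or for loss after month 6

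*Combined protocol and SAP*

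**What the plan says.** All of this is in Statistics (power analysis) unless another section is named.

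- **Power.** The secondary Power Calculations paragraph starts from "A sample size of 111 evaluable subjects at 6 months determined by the primary outcome". It then says that "we expect to observe 106 AEs in the 111 subjects completing a 12-month follow-up period", enters this rate into a macro described as "a Poisson power calculator", and concludes that "we will be able to detect a rate ratio of at least 1.70 with 80% power and 1.85 with 90% power".
- **Supporting ratio.** The same paragraph cites 136 against 76 AEs below and above the median step count in the team's observational data, a ratio of 1.79, and takes this as a sign of adequate power.
- **Analysis.** AEs are summed over the 12-month study period, and "negative binomial regression models (PROC GENMOD) will be used". Covariates are treatment, site, prior-year AE count and any unbalanced baseline characteristics. The text expects a Poisson distribution, gives no dispersion value and describes no offset for follow-up time.
- **Where 111 comes from.** Under the primary aim, "We anticipate a maximal drop-out of 40% at 6 months", and "In order to have 111 evaluable subjects at 6 months" 185 are enrolled (185 × 0.60 = 111). Work Proposed states that subjects "will be randomized with an allocation ratio of 1:1 to one of 2 arms".

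**The concern.** A power figure describes one test on one expected amount of information. Here both differ from the plan.

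A Poisson calculation sets the variance of a subject's count equal to its mean. The negative binomial model allows for subjects who differ in their underlying rate, which widens the standard error of the log rate ratio. The plan itself gives reason to expect such differences: the Baseline Visit section says that earlier AEs strongly predict later ones. The rule that AEs must be 14 days apart deals with repeat counting within a subject, not with differences between subjects.

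The 111 is a month-6 number used as a month-12 number.

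At stake is how the AE result is read. If power is described as adequate for a ratio near 1.79 and is in fact well below 80%, a null result could be taken as evidence that the programme does not affect exacerbations.

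**Working it through.** **Inputs from the plan.** 106 AEs, 111 subjects, 12 months (106/111 = 0.955 per subject-year); 1:1 allocation, so 55.5 per arm; ratios 1.70, 1.85 and 1.79. Alpha is 0.05, stated for the comparison of means; neither alpha nor sidedness is restated for AEs, so two-sided 0.05 is assumed (critical value 1.960).

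**1. Reproducing the stated pair.** Take 106/111 as the rate in the lower-rate arm and use the Poisson-regression (Signorini) formula:

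power = Φ{[√(N × rate) × ln RR − 1.960 × √4] / √(2 + 2/RR)}, with N × rate = 106.

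- RR 1.70: (5.463 − 3.920)/1.782 = 0.866, power 80.7%.
- RR 1.85: (6.334 − 3.920)/1.755 = 1.375, power 91.5%.

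The stated pair is reproduced. Total events on this reading are 53 × (1 + 1.70) = 143 to 53 × (1 + 1.85) = 151, not 106.

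**2. Taking 106 as the total over both arms**, which is the literal wording.

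- Variance of the log ratio 4/106 (SE 0.1943). RR 1.70: 0.5306/0.1943 − 1.960 = 0.772, power 78.0%. RR 1.85: 0.6152/0.1943 − 1.960 = 1.207, power 88.6%. Detectable ratios are 1.72 (80%) and 1.88 (90%).
- Wald variance with the events split in the ratio. RR 1.70: 1/66.74 + 1/39.26 = 0.04046, power 75.1%. RR 1.85: 1/68.81 + 1/37.19 = 0.04142, power 85.6%. Detectable ratios are 1.76 and 1.94.
- Exact conditional binomial: 74.4% and 86.0%.

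Across the two-sided formulas tried, power is about 74–78% at 1.70 and 86–89% at 1.85, a shortfall of about 1 to 6 points.

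**3. Adding overdispersion.** The dispersion k is assumed, because the documents give none. Variance = 1/e1 + 1/e2 + 2k/55.5, with 106 total events. Example, RR 1.70 and k = 0.5: 0.04046 + 0.01802 = 0.05847, SE 0.2418, 0.5306/0.2418 − 1.960 = 0.234, power 59.3%.

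| k (assumed) | Power at 1.70 | at 1.79 | at 1.85 | Ratio detectable at 80% |
|---|---|---|---|---|
| 0 | 75% | 82% | 86% | 1.76 |
| 0.1 | 72% | 79% | 83% | 1.81 |
| 0.25 | 67% | 74% | 78% | 1.88 |
| 0.5 | 59% | 67% | 71% | 1.99 |
| 1.0 | 48% | 56% | 60% | 2.21 |

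On the favourable reading of step 1, the Wald variance is 1/53 + 1/(53 × RR) + 2k/55.5. Power at 1.70 is then 87% at k = 0 and 77% at k = 0.25. Power at 1.79 is 84% at k = 0.25 and 76% at k = 0.5.

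**4. Loss after month 6** (assumed; lost subjects contribute nothing; Poisson, variance 4/E).

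| Loss of the 111 | Events | Power at 1.70 | at 1.85 |
|---|---|---|---|
| 5% | 100.7 | 75.9% | 87.0% |
| 10% | 95.4 | 73.6% | 85.2% |
| 20% | 84.8 | 68.6% | 80.9% |

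**The case against.** **The stated figures may be computed correctly.** The plan enters a rate into a named macro whose formula cannot be seen, and step 1 reproduces the pair. This stands. A reader might infer an arithmetic error, or even that the 111 subjects were entered as 111 events, since 111 events with equal-split variance also give 1.70 and 1.85. The documents do not support either inference: step 1 explains the pair without any mix-up, and on the literal total the Poisson shortfall is small and depends on the formula. What remains is an ambiguity. Step 1 needs 143 to 151 events where the text expects 106, and 106 is half of the 136 + 76 = 212 AEs cited in the same paragraph, which would fit a pooled rate but does not prove one.

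**Under Poisson, power at 1.79 is adequate.** It is 82% (Wald) to 85% (4/E) with 106 total events. That is correct, but it holds only with no overdispersion and no further loss.

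**The dispersion values are not from the plan, and adjustment for prior-year AEs may absorb part of the dispersion.** Both points stand. The size of the loss is therefore a sensitivity range, not an estimate.

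**Attrition may be milder than the plan allows.** The 40% is a maximum, and Minimizing Attrition and Handling Missing Data reports 0% to 4% loss at 12 months in the team's other COPD studies. The 185 − 111 = 74 early losses are credited with no events. An assumed 0.25 year each adds 74 × 0.25 × 0.955 = 17.7 events, about 124 in all, and Poisson power of about 84% at 1.70. This is a fair point, but the analysis text describes no offset that would let partial follow-up count correctly.

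**AEs are a secondary aim.** The sample size rests on 6-minute walk distance and is unaffected. That limits the consequence to interpretation.

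**Conclusion.** The concern holds as a mismatch, not as a proven miscalculation. The stated power is Poisson power for 111 twelve-month completers. The planned analysis is negative binomial, and 111 is the number expected at month 6. These two facts come from the documents and need no assumption.

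The size depends on unstated inputs. With 106 as the total, two-sided Poisson power is about 74–78% at 1.70 and 86–89% at 1.85. Overdispersion matters more than that gap: Wald power at 1.70 is about 67%, 59% and 48% for assumed k of 0.25, 0.5 and 1.0, and power at the cited 1.79 is already 79% at k = 0.1. If 106/111 is the lower-rate arm's rate there is more room, but power at 1.70 still falls to 77% at k = 0.25. The claim of adequate power is not supported as it stands. It would be equally wrong to adopt a detectable ratio of about 1.9 to 2.2 as the plan's figure, because that range only reflects chosen values of k.

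**What to change.** 1. Recompute the AE power with a negative binomial formula. Take the dispersion from the team's own AE data, as the residual after adjustment for prior-year AEs, and show a range around it.
2. Replace the 111 completers by expected person-time to month 12, with a stated assumption on loss between months 6 and 12 and with credit for partial follow-up.
3. Add the log of follow-up time as an offset to the negative binomial model, so that the analysis uses partial follow-up in the same way.
4. State whether 106/111 is the pooled or the reference-arm rate, and state alpha and sidedness.
5. Report the detectable ratio that results. Keep the statement that power is adequate only if that ratio supports it.

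The cost is one recalculation and a short change to the model text. The restated figure will probably be less favourable. No extra patients are needed and the primary sample size does not change.
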